The anterior segment will be examined through the slit lamp before performing IOP measurements, pachymetry, or graded assessments. The following structures will be evaluated as normal or abnormal. If abnormal, the findings should be described and recorded as either CS or NCS. Any CS findings should be recorded as AEs; the investigator may use his/her discretion to determine whether a finding considered NCS is reported as an AE. Findings and assessment of clinical significance should be recorded in the source documents and eCRF.

The following will be examined at each visit:

- Lids/lashes/lacrimal
- Conjunctiva
- Cornea
- Anterior chamber
- Iris
- Lens

Anterior Segment Graded Assessments

Anterior segment graded assessments will be performed at the following visits:

- Screening
- Midwashout assessment
- SDTP (Cohort A only): Days -2 and -1 and Days 1 and 2
- MDTP (all cohorts): Days -2 and -1 and Days 1, 2, 7, 14, 21, 27, 28, and 29

See [Table 2](#), [Table 3](#), [Table 4](#), and [Table 5](#) for detailed timings by cohort.

Anterior segment graded assessments should be performed during the slit lamp examination but before IOP measurement. The following assessments will be performed:

- Conjunctival redness score assessment
- Corneal haze assessment
- Corneal epithelial integrity assessment by fluorescein staining
- Anterior chamber cell and flare
- Lens opacification (performed during dilated examination only)

The procedures are outlined in [Appendix 2](#); full instructions are provided in the ophthalmology procedures manual.

Any abnormal findings should be described and recorded as either CS or NCS. Any CS findings should be recorded as AEs; the investigator may use his/her discretion to determine whether a finding considered NCS is reported as an AE. Findings and assessment of clinical significance should be recorded in the source document and eCRF.

Intraocular Pressure

Intraocular pressure will be measured at the following visits:

- Screening
- Midwashout assessment
- SDTP (Cohort A only): Days -2 and -1, Days 1 and 2
- MDTP (all cohorts): Days -2 and -1 and Days 1, 2, 7, 14, 21, 27, 28, and 29

See [Table 2](#), [Table 3](#), [Table 4](#), and [Table 5](#) for detailed timings by cohort.

Predose morning IOP assessments must be completed at least 30 minutes before dosing to allow the anesthetic to wear off.

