11.6.2.9 Intraocular Pressure

Intraocular pressure will be measured at the following visits:

- Screening
- Midwashout assessment
- SDTP (Cohort A only): baseline (Days -2 and -1), Days 1 and 2
- MDTP (all cohorts): baseline (Days -2 and -1) and Days 1, 2, 7, 14, 21, 27, 28, and 29.

See [Table 2](#), [Table 3](#), [Table 4](#), and [Table 5](#) for detailed timings by cohort. Two consecutive IOP measurements, to the nearest mmHg, will be made in the designated study eye; if the 2 measurements differ by more than 2 mmHg, then a third measurement will be performed. The procedure will be repeated in the nonstudy eye. All measurements will be recorded in the source document and eCRF and the mean of the (2 or 3) readings for each eye will be used to determine the mean IOP at the given time point for each eye. These mean IOP values will be used for all IOP analyses.

The baseline IOP is defined as the average of the mean IOP measurements at Day -1 and Day -2. A separate baseline will be derived for each scheduled timepoint. Descriptive statistics for IOP, the change from baseline, and the percentage change from baseline at each assessment time point

will be presented by eye (study eye vs. non-study eye) and treatment. Change from baseline will be calculated comparing post-treatment values to their respective baselines (e.g., on treatment pre-dose assessments will be compared to baseline pre-dose assessments, on treatment 1 hour assessments will be compared to baseline 1 hour assessments and on treatment 12 hour assessments will be compared to baseline 12 hour assessments). Line plots displaying mean IOP, change from baseline, and percent change from baseline at each visit and each scheduled timepoint will be presented by eye (study eye, non-study eye) and treatment for SDTP and MDTP. Line plots displaying mean IOP, at selected visits (baseline, Day 14 and Day 28) and selected scheduled timepoints (predose, +2h, +4h, +8h) during MDTP will be presented for study eye by treatment. Spaghetti plots showing the IOP values at each visit and each timepoint for all subjects in the Safety set will be presented by eye (study eye, non-study eye) and treatment for SDTP and MDTP.

Diurnal fluctuation in IOP will be summarized as below:

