- The baseline diurnal IOP (schedule 1) is defined as the average of all IOP measurements across three time points (predose, +2 h, +8 h) at Day -1 and Day -2. Postbaseline diurnal IOP is defined as the average of all IOP measurements across three time points (predose, +2 h, +8h) at each visit. Change from baseline will be calculated as the difference between postbaseline diurnal IOP and baseline diurnal IOP. Descriptive statistics for diurnal IOP, the change from baseline, and the percentage change from baseline at each visit will be presented by eye (study eye, non-study eye) and treatment.
- The baseline diurnal IOP (schedule 2) is defined as the average of all IOP measurements across three time points (predose, +4 h, +8 h) at Day -1 and Day -2. Postbaseline diurnal IOP is defined as the average of all IOP measurements across three time points (predose, +4 h, +8h) at each visit. Change from baseline will be calculated as the difference between postbaseline diurnal IOP and baseline diurnal IOP. Descriptive statistics for diurnal IOP, the change from baseline, and the percentage change from baseline at each visit will be presented by eye (study eye, non-study eye) and treatment.

Results of intraocular pressure will be listed by individual subject.

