12.4 Pharmacodynamic Methods

All the PD analyses will be performed using the Pharmacodynamic set. Intraocular pressure (IOP; mmHg), a PD biomarker, will be measured using Goldmann applanation tonometry.

Intraocular pressure will be measured according to the following schedule:

SDTP (Cohort A only): baseline (Days -2 and -1), Days 1 and 2, at Predose, 0.5, 1, 2, 3, 4, 6, 8, and 12 h

MDTP (Cohort A only): (all cohorts): baseline (Days -2 and -1), Days 1, 2, 27, and 28, at Predose, 0.5, 1, 2, 3, 4, 6, 8, and 12 h

MDTP (all cohorts): Days 7, 14, and 21 at Predose, 2, 4, 8, and 12 h

The individual and mean absolute IOP, IOP reduction from baseline and percentage of IOP reduction from baseline versus time profiles will be presented in figures. Mean plots will be presented using nominal time and individual plots will be presented using actual time.

In addition, the relationship of percentage of IOP reduction from baseline and dose of SHP639 will be presented in a Box-and-Whiskers plot.

Percentage of IOP reduction from baseline measurements data versus time will be used to estimate the PD parameters using Phoenix® WinNonlin® version 6.4 (Certara USA, Inc., Princeton, NJ) for each individual in each treatment by eye (study eye and non-study eye). Baseline is defined as the arithmetic mean of the time-matched IOP measurements on Days -2

and -1 for that particular subject. Potential effect of diurnal change on variation in IOP is accounted for by factoring time-matched baseline in the calculations of percent of IOP reduction from baseline measurements.

Parameter	Definition
IOP reduction from baseline	IOP reduction from baseline is calculated as follows: $\frac{\text{Baseline IOP} - \text{IOP after treatment}}{\text{Baseline IOP}}$
% of IOP reduction from Baseline	Percentage of IOP reduction from baseline is calculated as follows: $\frac{(\text{Baseline IOP} - \text{IOP after treatment})}{\text{Baseline IOP}} \times 100$
E _{max}	Maximum percent IOP reduction from baseline
TE _{max}	Time of E _{max}
AUEC _{0-t}	Area under the effect curve for the percentage of IOP reduction from baseline versus time profile from time zero (predose) to the time of the last measurable percentage of IOP reduction from baseline, calculated using the linear up/log down interpolation rule.
AUEC _{0-τ}	Area under the effect curve for the percentage of IOP reduction from baseline versus time profile over a dosing interval, calculated using the linear up/log down interpolation rule.

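### On Day 1 of each treatment period the SAP's diurnal IOP includes a reading taken before that period's first dose, so the diurnal tables understate the post-dose reduction by one third in mmHg when no predose change is expected

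*SAP*

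**What the plan says.** SAP 11.6.2.9 defines two diurnal averages. For schedule 1, "Postbaseline diurnal IOP is defined as the average of all IOP measurements across three time points (predose, +2 h, +8h) at each visit". For schedule 2, "Postbaseline diurnal IOP is defined as the average of all IOP measurements across three time points (predose, +4 h, +8h) at each visit". The matching baselines are the averages at the same three times over Days -2 and -1, and "Change from baseline will be calculated as the difference between postbaseline diurnal IOP and baseline diurnal IOP".

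The same section lists Day 1 as an IOP visit in both treatment periods. It fixes the reference days for IOP in general: "The baseline IOP is defined as the average of the mean IOP measurements at Day -1 and Day -2". The Day 1 predose value is therefore not part of baseline.

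SAP 12.4 schedules predose, 2, 4 and 8 h readings on Day 1 of both periods, so both averages can be formed. Protocol 7.2.2.3 places the first of these before drug: "Predose morning IOP assessments must be completed at least 30 minutes before dosing". Nothing in either document treats Day 1 differently from later visits.

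The results go into Tables 14.3.7.9.3 to 14.3.7.9.6 (SDTP) and 14.3.7.9.9 to 14.3.7.9.12 (MDTP).

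**The concern.** From Day 2 of the MDTP the predose reading is a trough on treatment and belongs in a diurnal mean. On Day 1 it is a reading before that period's first dose, yet it carries a third of the weight in what is presented as the postbaseline value.

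In the SDTP this affects the main result in the table. Drug is given once, on Day 1, and Day 2 is a non-dosing day (SAP 15.8), so Day 1 is the only dosing-day entry in those four tables. In the MDTP the predose component changes meaning between Day 1 and Day 2, which can affect how the time course reads.

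IOP reduction is the secondary objective. The MDTP diurnal tables are flagged as interim outputs in SAP section 16, and Protocol 9.5 says the interim is meant to show whether a dose with a worthwhile pharmacodynamic effect has been found. The footnote to the study schema in SAP 2.1 includes IOP among the data used in escalation decisions.

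**Working it through.** The documents give no figure for this, so there is nothing to reproduce. The mmHg values below are assumptions; the one-third ratio does not depend on them.

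**Weights.** SAP 11.6.2.9 first averages the two or three readings at each time point and uses those means in all IOP analyses. Each time point therefore has weight 1/3. If raw readings were pooled instead, the predose weight would lie between 2/8 = 25% and 3/7 = 43%.

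**General result, schedule 1.** Let c0, c2 and c8 be the time-matched changes from baseline at predose, +2 h and +8 h.

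- SAP diurnal change = (c0 + c2 + c8)/3
- Post-dose change = (c2 + c8)/2
- With c0 = 0, the ratio is [(c2 + c8)/3] / [(c2 + c8)/2] = 2/3, whatever c2 and c8 are.

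For c2 = c8 = -4 the SAP gives -8/3 = -2.67 mmHg against -4.00. Schedule 2 is the same with c4 in place of c2.

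**Worked example.** Assume baselines of 26, 24 and 23 mmHg at predose, +2 h and +8 h, and a 20% fall after dosing.

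- Baseline mean: (26 + 24 + 23)/3 = 24.33
- Day 1 mean: (26 + 19.2 + 18.4)/3 = 21.20
- Reported fall: 24.33 - 21.20 = 3.13 mmHg, or 12.9%
- Post-dose fall: 0.2 × (24 + 23)/2 = 4.70 mmHg, or 20%

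**Percentage change.** The loss is a little larger when the predose baseline is the highest of the three. For a 4 mmHg fall, baselines of 24/24/24 give 11.1% against 16.7% (a loss of 33%), and 26/22/20 give 11.8% against 19.0% (a loss of 38%).

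**If c0 is not zero.** Suppose a drift r affects all time points in both arms, with drug effect e after dosing. The SAP change is r + 2e/3 and the post-dose change is r + e. With e = -4, the raw understatement falls from 33% at r = 0 to 22% at r = -2 (-4.67 against -6.00). The placebo-adjusted effect is 2e/3 against e, so that loss stays at 33.3%. A simulation that applied the Day -1 entry thresholds of 24 and 22 mmHg (assumed mean 25, between-subject SD 2, within-subject SD 1.5, effect 4 mmHg) gave a mean predose drift of -0.14 mmHg. The raw changes were -2.73 against -4.03, and the placebo-adjusted changes -2.67 against -4.00.

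**Day 1 against later MDTP visits.** This uses the same baselines and a constant 20% effect at +2 and +8 h, varying only the effect left at trough.

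| Effect at trough | Day 1 as planned | Later visit as planned | Two-point mean, every visit |
|---|---|---|---|
| none | 3.13 | (0 + 4.8 + 4.6)/3 = 3.13 | 4.70 |
| half (10%) | 3.13 | (2.6 + 4.8 + 4.6)/3 = 4.00 | 4.70 |
| full (20%) | 3.13 | (5.2 + 4.8 + 4.6)/3 = 4.87 | 4.70 |

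As planned, the apparent build-up ranges from nothing to 1.74 mmHg (4.87 - 3.13), although the post-dose effect never changes.

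**The case against.** The strongest objection is that the undiluted result is already planned. SAP 11.6.2.9 reports time-matched change and percentage change at every time point, with line and spaghetti plots for both periods. SAP 12.4 and 12.5 analyse reduction by nominal time on the PD set, without any diurnal mean. The diurnal averages are descriptive Safety-set summaries, and the SDTP ones are not interim outputs. With no expected predose change, the mmHg factor is the same in every dose group, so Day 1 dose ranking is preserved. All of this stands, and it limits the point to the diurnal tables. It does not correct those tables, where a reader cannot see the dilution.

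A second objection is that Day 1 predose is literally after the Day -2/-1 baseline and is openly named as a component. That is true of the label, but the tabulated change is still a diluted measure of response to the dose.

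A third concerns the remedy. Using two points on Day 1 and three later would create a new artefact: with no trough effect, 4.70 then 3.13 mmHg, a false loss. This is right, and the fix has to avoid it.

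Finally, table specifications are in a separate document, so the visits displayed are not known, and Day 29 has only one IOP time. This limits where the rule can apply but does not exempt Day 1.

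A reader might also infer more than the documents support:

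- *That the trial's first-dose effect is understated throughout.* It is not; the analyses listed above are unaffected.
- *That the MDTP must show a false build-up.* That requires effect at trough, which is not known. The duration the Protocol reports, at least 8 hours at the highest dose tested, is from rabbits.
- *That the MDTP Day 1 predose reading is drug-naive in every cohort.* In Cohort A the study eye has had a single dose, followed by a 3-14 day washout.
- *That Emax is diluted in the same way.* It is a maximum, not a mean, and the shift in treated subjects is close to zero.

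**Conclusion.** The point holds for the diurnal IOP tables on SDTP Day 1 and MDTP Day 1. The stated rule understates the post-dose reduction by exactly one third in mmHg if the expected predose change is zero, and by 33% to 38% in percentage terms for the baselines tried. Under drift common to both arms and all time points, the placebo-adjusted mmHg loss is still one third. Distortion of the MDTP time course is possible, but its size depends on the unknown trough effect.

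The change is worth making because Day 1 is the only dosing day in the SDTP diurnal tables and the MDTP diurnal tables feed an interim review of pharmacodynamic effect. It does not call the PD analysis or the safety conclusions into question.

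**What to change.** Amend SAP 11.6.2.9 as follows.

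- **SDTP Day 1:** define diurnal IOP as the mean of the post-dose points (+2 and +8 h for schedule 1; +4 and +8 h for schedule 2), compared with the Day -2/-1 mean at the same two points.
- **MDTP:** report that same two-point mean, with its matched baseline, at every visit with the full set of times, including Day 1. Under SAP 12.4 these are Days 1, 2, 7, 14, 21, 27 and 28. Keep the three-point mean including trough from Day 2 onward as a separate row.
- **Comparisons:** state that a two-point Day 1 value is not to be compared with three-point values at later visits. Time-course statements should use the two-point row throughout.

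The cost is a few lines of SAP text, a small programming change and one extra summary row in the MDTP tables. No new data are needed. The downside is that the Day 1 value rests on two time points instead of three, so it will be somewhat less precise.

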11.6.2.10 Posterior Segment Examination

The posterior segment will be visualized by a fundus examination at the following visits:

- Screening – dilated
- SDTP baseline (Cohort A only) – nondilated (Day -2)
- MDTP baseline – nondilated (Day -2)
- Day 29 – dilated.

A dilated posterior segment examination of both eyes should also be performed if the BCVA in either eye decreases by 6 or more letters.

The following structures will be assessed (suggested technique):

- Vitreous (binocular indirect examination)
- Optic nerve head (slit lamp biomicroscopy)
- Cup-to-disc ratio (slit lamp biomicroscopy)
- Macula (slit lamp biomicroscopy)
- Retina vasculature
- Retinal, outside of arches, including periphery
- Choroid

The number and percentage of subjects who have normal results and abnormal results for vitreous, disc, macula, retinal vasculature, retina, and choroid will be summarized by eye (study eye, non-study eye, and either eye (MDTP only)), treatment group and time point. For either eye summaries, a subject will be counted as normal only if both eyes are normal and as abnormal if either eye is abnormal. The denominator of the percentage is the number of subjects who have assessment for the specified eye and visit. In addition, the number and percentage of subjects with clinically significant abnormal results, and non-clinically significant abnormal results will be summarized by treatment. Also, the number and percentage of subjects with at least one postbaseline abnormal finding and at least one post baseline clinically significant abnormal finding for each assessment type will be summarized

Descriptive statistics for the horizontal and vertical cup to disc ratios and their changes from baseline at each assessment time point will be presented by eye (study eye, non-study eye, and either eye (MDTP only)) and treatment. Baseline disc ratio is defined as the Day -2 screening assessment. For either eye summaries, the eye with the greater disc ratio will be summarized at baseline. For post baseline assessment, the eye with the greater increase from baseline will be summarized. If both eyes have the same change from baseline, the eye with the greater value will be summarized.

The number and percentage of subjects who have no notch at baseline and a notch present at any time during post baseline period will be summarized by eye (study eye, non-study eye, and either eye (MDTP only)) and treatment. Only subjects who have no notch at baseline will be included in this summary. Baseline notch presence is defined as the Day -2 baseline assessment. For either eye summaries, a subject will be counted as notch absent if both eyes have no notch and as notch present if either eye has a notch. The percentages will be calculated relative to the number of subjects with available baseline notch assessment and at the postbaseline assessment for the given timepoint.

In addition, the number and percentage of subjects with changes in number of notches from baseline in the following categories by treatment group will be presented:

- 0 (no change)
- 1+ (increase by 1 notch)
- 2+ (increase by 2 notches)

- 3+ (increase by 3 notches)
- 4+ (increase by 4 notches)

The percentage will be calculated relative to the number of subjects with available baseline notch assessment and at the postbaseline assessment for the given timepoint. For either eye summaries, the eye with greatest increase in number of notches will be summarized.

Results of posterior segment examination will be listed by individual subject and a separate listing of clinically significant findings will also be presented.

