4.1 Inclusion Criteria

The subject will not be considered eligible for the study without meeting all of the criteria below.

Subjects cannot be enrolled or randomized before all inclusion criteria (including test results) are confirmed.

1. Subjects must provide written, signed and dated informed consent to participate in the study in accordance with the International Council for Harmonisation (ICH) Good Clinical Practice (GCP) Guideline E6 and applicable regulations, before completing any study-related procedures.
2. Subjects must be aged from 18 through 90 at the time of consent. This inclusion criterion will only be assessed at the screening visit.
3. Subjects must have OHT or stable early POAG in both eyes with acceptable Humphrey visual fields (HVF). Early POAG for this protocol is defined as healthy appearing anterior chamber angles (Shaffer classification system grade 3 or 4) and focal and/or generalized thinning of the optic disc rim characteristic of glaucomatous disease. An acceptable HVF must have been performed within approximately one year of screening, have a false-positive rate of 25% maximum, false-negative rate of 25% maximum, and fixation loss rate of 33% maximum, and mean deviation of no worse than -6.00 dB.
4. On Day -1, subjects must have a mean IOP of ≥ 24 mmHg at 8:00 AM and a mean IOP of ≥ 22 mmHg at 10:00 AM in at least 1 eye, with an IOP difference of < 4 mmHg between eyes at both of these time points. If only 1 eye meets this criterion, then it will be the designated study eye for pharmacodynamic analysis; this eye will also be used for dosing in Cohort A SDTP (designated study eye criteria are detailed in Section 3.1.1).
5. Subjects must have a best-corrected visual acuity (BCVA) in both eyes of 65 letters on the Early Treatment Diabetic Retinopathy Study chart (Snellen equivalent $\sim 20/60$) or better at the screening and baseline assessments.
6. Subjects must be males or females who are nonpregnant and nonlactating at screening (negative serum beta-human chorionic gonadotropin [β -hCG]); if sexually active during the study, they must agree to comply with the applicable contraceptive requirements (refer to Section 4.4) throughout the study period and for 60 days following the last dose of investigational product.

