Intraocular pressure will be measured at the slit lamp using Goldmann applanation tonometry. The procedure for measuring IOP is outlined in the ophthalmology procedures manual. Special care must be taken to avoid placing pressure on the globe with the fingers when moving the eyelids to fully expose the cornea.

Intraocular pressure must be measured after assessing the corneal epithelium for fluorescein staining and before pachymetry, gonioscopy, or dilation for posterior segment examination (if being performed).

Two consecutive IOP measurements, to the nearest mmHg, will be made in the designated study eye (designated study eye criteria are detailed in Section [3.1.1](#)); if the 2 measurements differ by more than 2 mmHg, then a third measurement will be performed. All (2 or 3) readings will be used to determine the mean IOP at the given time point. The procedure will be repeated in the nonstudy eye. All measurements will be recorded in the source document and eCRF.

Every effort should be made to obtain an accurate IOP measurement. If the mires are irregular and/or an IOP reading is not obtainable, this should be noted in the source document and eCRF.

Posterior Segment Examination

The posterior segment will be visualized by a fundus examination at the following visits:

- Screening – dilated
- SDTP– nondilated Day -2

- MDTP– nondilated Day -2
- Day 29 – dilated

A dilated posterior segment examination of both eyes should also be performed if the BCVA in either eye decreases by 6 or more letters.

The following structures will be assessed (suggested technique):

- Vitreous (binocular indirect examination)
- Optic nerve head (slit lamp biomicroscopy)
- Cup-to-disc ratio (slit lamp biomicroscopy)
- Macula (slit lamp biomicroscopy)
- Retina vasculature
- Retina, outside of arcades, including periphery
- Choroid

Observations will be described and/or will be graded as normal or abnormal. Abnormal findings will be described. Clinically significant abnormalities will be recorded as AEs; NCS findings will be recorded as AEs at the investigator's discretion. Further details will be specified in the ophthalmology procedures manual.

Gonioscopy

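### Posterior segment tables: the notch baseline is an undilated exam set against a dilated Day 29 exam, the cup-to-disc baseline is ambiguous, and entry disease counts as post-baseline abnormality

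*SAP*

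**What the plan says.** Protocol 7.2.2.3 and SAP 11.6.2.10 give the same exam schedule. In the SAP's list the pre-treatment exam is "Screening – dilated". The Day -2 exams of the single-dose and multiple-dose periods (SDTP and MDTP) are both undilated; the MDTP entry begins "MDTP baseline – nondilated (Day -2". The protocol's final exam is "Day 29 – dilated".

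SAP 11.6.2.10 then defines three kinds of summary:

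- **Cup-to-disc ratio.** Change from baseline is summarized, with "Baseline disc ratio is defined as the Day -2 screening assessment".
- **Notches.** "Baseline notch presence is defined as the Day -2 baseline assessment". One table takes subjects without a notch at baseline and counts those with a notch later. Another sorts subjects by change in notch number, in categories from no change up to an increase of 4.
- **Fundus structures** (vitreous, disc, macula, vessels, retina, choroid). Normal and abnormal results are shown by time point. The SAP adds "the number and percentage of subjects with at least one postbaseline abnormal finding and at least one post baseline clinically significant abnormal finding", for each type of assessment.

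Protocol 4.1, criterion 3, defines early primary open-angle glaucoma partly by "focal and/or generalized thinning of the optic disc rim characteristic of glaucomatous disease". Exclusion criterion 9 in Protocol 4.2 allows early nonproliferative diabetic retinopathy and early dry macular degeneration.

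**The concern.** A change from baseline is easiest to read when both exams are done in the same way. Here the notch baseline is taken through an undilated pupil and the follow-up through a dilated one, so a notch missed at Day -2 and seen at Day 29 is tabulated as new. For the cup-to-disc ratio, the sentence that should settle the question names two different visits.

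Separately, a table of post-baseline abnormalities that ignores baseline status mixes disease the subject brought into the trial with anything that arose on treatment.

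Safety is the primary objective. The MDTP fundus, cup-to-disc and new-notch tables are flagged as interim outputs in SAP 16, and Protocol 9.5 says the interim is meant to help identify a safe and tolerable dose. In cohorts this small, one or two subjects counted for the wrong reason change how a table reads.

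**Working it through.** The plan states no figure to reproduce. The check sets the passages side by side, with simple arithmetic at the end.

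**1. State of each scheduled exam** (Protocol 7.2.2.3; SAP 11.6.2.10; SAP Table 10)

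| Exam | SAP window | Pupil |
|---|---|---|
| Screening | Day -42 to Day -3 | dilated |
| Day -2 (SDTP, MDTP) | Day -2 | undilated |
| Day 29 | Day 29 | dilated |

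The unscheduled exam triggered by a loss of 6 or more letters of acuity is also dilated. No posterior segment exam is scheduled after the dose in the SDTP, so the point concerns the MDTP.

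**2. Cup-to-disc ratio.** If the baseline is Day -2, change is undilated to dilated. If it is Screening, change is dilated to dilated. Table 10 makes these separate visits, so the sentence cannot mean both.

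**3. Notches.** The baseline is Day -2 without ambiguity. Two cases follow if the disc itself does not change:

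- Not seen at Day -2, seen at Day 29: counted as a new notch, and as an increase.
- Seen at Day -2, not seen at Day 29: left out of the new-notch table. In the change table the subject is in the denominator but has no row.

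The either-eye rules take the eye with the greater increase, which leans the same way. By contrast, SAP 11.6.2.4 tabulates conjunctival redness change from -4 to +4.

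**4. Fundus structures.** No change from baseline is defined. The count of subjects with at least one post-baseline abnormality requires neither a normal baseline nor worsening. A subject with stable rim thinning, early diabetic retinopathy or early dry macular degeneration, graded abnormal at both visits, is counted. The SAP is stricter elsewhere: SAP 11.4 bases the ECG percentages on subjects whose baseline value was not already potentially clinically important, and SAP 11.1 requires a treatment-emergent event to start or worsen after first dose.

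**5. Weight of one subject** (SAP 2.3 and 11)

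- Active, per cohort: 1/5 = 20%.
- Placebo pooled by regimen: 3 × 2 = 6 subjects, 1/6 = 17%. For the four-times-daily regimen, with Cohort D1 not enrolled, 2 × 2 = 4 subjects, 1/4 = 25%. Both are before any repeat cohort or replacement.

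**6. Age of the Screening exam** (Protocol 3.2)

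- Cohorts B, C, D: up to about 42 days before first dose.
- Cohort A: 42 + 2 (SDTP) + 14 (second washout) = about 58 days before MDTP dosing, with a single dose in between.

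**The case against.** There is a fair case for Day -2. It follows the washout of pressure-lowering drops, which Protocol 7.1.1.3 places within the screening period, whereas the Screening exam may precede it. Day -2 is close to dosing. It also fits the SAP's pattern of separate SDTP and MDTP baselines, and in Cohort A a Screening baseline would sit before the single dose. This argument stands, and it is why Day -2 should not simply be replaced.

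Three stronger readings are tempting and are not supported:

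- *True new findings cannot be told apart from artefact.* They can, in large part. Clinically significant posterior segment abnormalities are recorded as adverse events (Protocol 7.2.2.3) and pass through the treatment-emergent rule. Ocular history is summarized by eye (SAP 8). By-visit tables, subject listings and a listing of clinically significant findings are planned. Subjects with a notch recorded at baseline are excluded from the new-notch table.
- *All fundus changes suffer from the dilation mismatch.* The SAP defines no change from baseline for the fundus structures, so the mismatch there appears only when visit columns are compared. For cup-to-disc ratio, what is shown is a contradictory label.
- *A rate of false new findings can be stated.* The documents give no figure for how far dilation alters notch or cup-to-disc readings, and do not say that undilated readings are unreliable. Any probability would rest on an invented rate.

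The mismatch also falls on active and placebo alike, so it distorts absolute change and incidence more than the contrast between groups. With about 6 placebo subjects per regimen, however, that contrast is too imprecise to remove the artefact reliably.

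**Conclusion.** The point holds in four specific parts. The notch baseline and the Day 29 exam are done under different conditions although a matching dilated pre-dose exam exists. The cup-to-disc baseline names two visits at once. A decrease in notches has no category. The post-baseline abnormality count includes stable disease that the eligibility criteria admit.

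The first part matters only if dilation affects what is seen. The documents suggest that they regard dilation as relevant: Protocol Table 1 confines lens grading to the dilated exams, and a loss of acuity calls for a dilated fundus exam. They give no size or direction, and none is claimed here. The other three parts follow from the wording alone. The size that can be stated is that one subject counted in this way is 20% of a 5-subject active group.

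These are descriptive tables with partial safeguards elsewhere in the SAP. The correction is worth making because it is cheap and concerns the primary objective; trial conduct is unaffected.

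**What to change.** In SAP 11.6.2.10:

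1. Name one exam as the cup-to-disc baseline by deleting either the day or the word screening. For cup-to-disc ratio, notch presence and notch number in the MDTP, present Day 29 against the dilated Screening exam, with the comparison against Day -2 alongside.
2. Add, for each fundus structure, the number and percentage of subjects with a new or worsened abnormality: abnormal after baseline, and normal or less severe at the dilated pre-dose exam. The SAP records normal or abnormal and clinical significance, so worsened could be defined as a move from not clinically significant to clinically significant. The existing count can stay if its title says that it includes abnormalities present at entry.
3. Add a category for a decrease in number of notches, so that the rows account for everyone in the denominator.

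The cost is SAP wording, extra table columns and re-derivation; no new data are collected. The drawback is the age of the Screening exam (about 42 days, or about 58 in Cohort A with one dose in between) and its possible timing before washout. Showing both comparisons makes that visible. SAP 13 records that an interim on the repeat of Cohort B3 has already been run, so the new summaries should be described as additions, so that interim and final outputs can be reconciled.
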